7.3 Exploratory analyses

The univariate associations between demographic, co-morbid and perioperative factors (including anaesthesia depth, BIS, MAP and MAC) and POD will be firstly undertaken using univariate logistic regression analyses. Factors identified from these analyses as showing some association with POD ($p < 0.15$) will then be entered into multivariate forward and backward logistic regression models to identify a model containing those measures which are independently associated with POD. Adjusted Odds ratios and 95% confidence intervals will be derived from these models.

The univariate associations between demographic, co-morbid and perioperative factors (including anaesthesia depth, BIS, MAP and MAC) and POD severity will be firstly undertaken using 1-way ANOVA and Pearson's correlation coefficients. Factors identified from these analyses as showing some association with POD severity ($p < 0.15$) will then be entered into multivariate forward and backward linear regression models to identify a model containing those measures which are independently associated with POD severity. Adjusted means and regression coefficients with 95% confidence intervals will be derived from these models. If the distribution of POD severity does meet the assumptions for these analyses then the data may be square root transformed prior to the analyses.

The univariate associations between demographic, co-morbid and perioperative factors (including anaesthesia depth, BIS, MAP and MAC) and MMSE changes and AMTS levels will be firstly undertaken using 1-way ANOVA and Pearson's correlation coefficients. Factors identified from these analyses as showing some association with MMSE and AMTS ($p < 0.15$) will then be entered into multivariate forward and backward linear regression models to identify a model containing those measures which are independently associated with MMSE and AMTS. Adjusted means and regression coefficients with 95% confidence intervals will be derived from these models.

The association between any POD diagnosis and the clinical outcomes, any cardiovascular event (MI, cardiac arrest, stroke, PE) and any infection during 1 year follow-up will firstly be tested using a chi-square test. Following this multivariate models will be developed for these clinical outcomes using demographic, co-morbid and perioperative factors (including anaesthesia depth, BIS, MAP and MAC), to which a POD diagnosis will be added.

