4.3 Participant populations

Approximately 600 participants from 8 sites in Australia, Hong Kong, USA and China will be enrolled in the study.

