7 EFFICACY ANALYSES

7.1 Primary endpoint analyses

The primary endpoint analysis will compare the primary endpoint, diagnosis of delirium at any post-operative assessment, in the intention-to-treat population, using a Mantel-Haenszel Chi-square test, stratified by study-centre groups. The pooled estimate of the odds ratio and 95% confidence interval from this analysis will be used to summarise the statistical comparison. Analyses will be undertaken on both the Intention-to-Treat population and the Per-Protocol populations.

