7.2 Secondary endpoint analyses

The analysis of the secondary endpoint the incidence of POD at each assessment time will be undertaken as supporting analyses of the primary

endpoint. These analyses will compare POD between randomised groups at each post-operative assessment, in the intention-to-treat population, using a Mantel-Haenszel Chi-square test, stratified by study-centre groups. The pooled estimate of the odds ratio and 95% confidence interval from this analysis will be used to summarise the statistical comparison. Analyses will be undertaken on both the Intention-to-Treat population and the Per-Protocol populations.

The analysis of the secondary endpoint the severity of POD, in the intention-to-treat population, will be undertaken using a general linear model with study-centre and randomized groups as fixed factors in the model. The mean difference between randomised groups derived from the model will be presented with the 95% confidence interval. If the distribution of the severity does not meet the assumptions for this parametric analysis then the severity maybe square root transformed prior to analysis. Analyses will be undertaken on both the Intention-to-Treat population and the Per-Protocol populations.

The analysis of the secondary endpoint the change in MMSE score at discharge, in the intention-to-treat population, will be undertaken using a general linear model with randomised group and study-centre as fixed factors in the analysis. The mean difference in the changes between randomised groups derived from the model will be presented with the 95% confidence interval. Analyses will be undertaken on both the Intention-to-Treat population and the Per-Protocol populations.

The analysis of the secondary endpoint the AMTS level at 3 and 12 months, in the intention-to-treat population, will be undertaken using a general linear model with randomised group and study-centre as fixed factors in the analysis. The mean difference in the levels between randomised groups derived from the model will be presented with the 95% confidence interval. Analyses will be undertaken on both the Intention-to-Treat population and the Per-Protocol populations.

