The analysis of the secondary endpoint cognitive impairment at discharge (MMSE < 26) or at 3 and 12 months (AMTS<8) will be undertaken, in the intention-to-treat population, using a Mantel-Haenszel Chi-square test, stratified by study-centre groups. The pooled estimate of the odds ratio and 95% confidence interval from this analysis will be used to summarise the statistical comparison. Analyses will be undertaken on both the Intention-to-Treat population and the Per-Protocol populations, with all those identified as having cognitive impairment pre-operatively (MMSE < 26) excluded from the analyses.

The associations between POD incidence and subsequent MMSE changes at discharge and the AMTS levels at 3 and 12 months will be tested using a general linear model which will include randomised group, centre-stratum and

POD diagnosis as fixed factors and the MMSE change as the dependent variable.

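### The exploratory analyses in section 7.3 specify no centre term, although every analysis in 7.1 and 7.2 has one, so a site difference can be reported as an independent predictor

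*Combined protocol and SAP*

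**What the plan says.** Section 4.3 expects about 600 participants from "8 sites in Australia, Hong Kong, USA and China".

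Centre appears throughout the main analyses:

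- Section 7.1, primary endpoint: analysed "using a Mantel-Haenszel Chi-square test, stratified by study-centre groups". Section 7.2 uses the same test for delirium at each assessment and for cognitive impairment.
- Section 7.2, delirium severity: "general linear model with study-centre and randomized groups as fixed factors in the model".
- Section 7.2, MMSE change and AMTS level: "general linear model with randomised group and study-centre as fixed factors in the analysis".
- Section 7.2, delirium against later cognition, which is not a randomised comparison: a "general linear model which will include randomised group, centre-stratum and" delirium diagnosis.

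Section 7.3 names neither centre, site nor country. The delirium models begin with a screen in which the links between patient or perioperative factors (depth, BIS, MAP and MAC are named) "and POD will be firstly undertaken using univariate logistic regression analyses". Factors with p<0.15 then go into forward and backward selection. Severity, MMSE change and AMTS level follow the same route, with 1-way ANOVA and Pearson correlation as the screen. The association of delirium with cardiovascular events and infection "during 1 year follow-up will firstly be tested using a chi-square test", followed by multivariable models built from the same kinds of factor.

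**The concern.** The plan adjusts for centre where randomisation already gives protection, and leaves it out where there is none. Section 4.1 stratifies randomisation by country, so the arms in 7.1 and 7.2 should not be confounded with site to any important degree. The exposures in 7.3 are different. Apart from allocated depth, achieved BIS, MAP and MAC are not randomised. Nor are the baseline variables of section 5 that would be natural candidates, such as ethnicity and surgery type. All of these could differ between sites.

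Recorded delirium could differ too. Section 3.2 assesses it twice daily for 5 days or until discharge. If discharge timing varied by site (an assumption), so would the number of chances to record it. The severity measure, a count of episodes, would shift directly.

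If factor and outcome both vary by site, pooled tests and coefficients mix within-site with between-site differences. The exploratory objectives in section 3.4 seek factors independently associated with delirium, its severity and cognition, and the association of delirium with one-year events. A site difference could be read as any of these.

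**Working it through.** **1. Side by side.** The analyses in 7.1 and 7.2 are the primary endpoint, delirium at each assessment, severity, MMSE change, AMTS level, cognitive impairment, and delirium against cognition. All seven carry a centre term. The four sets in 7.3 are delirium, severity, MMSE/AMTS, and delirium against one-year outcomes. None carries one. Two contrasts are direct:

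- Severity has centre as a fixed factor in 7.2 but 1-way ANOVA and Pearson correlation in 7.3.
- Delirium as an exposure is adjusted for centre against cognition in 7.2, but tested by plain chi-square against one-year events in 7.3.

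**2. The plan's own figure.** Section 7.3 contains no figure that bears on centre. The one design figure, about 270 per group in section 4.2, reproduces:

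- n = [1.96√(2×0.20×0.80) + 0.8416√(0.25×0.75 + 0.15×0.85)]² / 0.10² ≈ 250.
- With continuity correction: (250/4)[1 + √(1 + 4/(250×0.10))]² ≈ 270.

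This point does not depend on it.

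**3. Size, on assumed inputs.** From the documents: 600 patients, 8 sites, and delirium at 20% (midpoint of 25% and 15%). Assumed: equal sites of 600/8 = 75, the centre ICCs below, and no effect of the factor within any site. The pooled score test (asymptotically equivalent to univariate logistic regression) was compared by simulation with its centre-stratified counterpart.

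As a check on the simulation, the variance of the pooled statistic is inflated by about D = 1 + (75 − 1) × ICC(delirium) × ICC(factor), so the false-positive rate is about 2[1 − Φ(1.96/√D)].

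| Delirium ICC | Expected lowest and highest site rate | D at factor ICC 0.05 / 0.5 | Formula | Simulated, pooled |
|---|---|---|---|---|
| 0.02 | about 13% and 29% | 1.074 / 1.74 | 5.9% / 13.7% | about 6% to 12% |
| 0.05 | about 9% and 34% | 1.185 / 2.85 | 7.2% / 24.6% | about 7% to 23% |
| 0.10 | about 6% and 40% | 1.37 / 4.70 | 9.4% / 36.6% | about 9% to 34% |

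The formula runs a little high at the upper end because there are only eight sites. With centre stratification the simulated rate is about 5% throughout. At delirium ICC 0.05, the chance that a null factor passes the p<0.15 screen is 18.8%, 19.2%, 31.0% and 37.2% for factor ICC 0.05, 0.1, 0.3 and 0.5.

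**4. The same question with fixed site rates.** Logistic regression with and without centre indicators, at p<0.05; 5%, 10% and 30% are the between-site shares of the factor's variance.

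| True site rates | Without centre: 5%, 10%, 30% | With centre |
|---|---|---|
| all 20% | 0.04-0.05 | 0.05 |
| 15% to 25% | 0.05-0.06 | 0.05 |
| 10% to 30% | 0.05, 0.08, 0.12 | 0.04-0.07 |
| 5% to 35% | 0.08, 0.12, 0.21 | 0.04-0.05 |

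**5. Delirium against a one-year event.** With an assumed 25% event rate and ICCs of 0.02 to 0.10, the plain chi-square rejects a true null in 5.2% to 11.8% of runs; the centre-stratified test in 4.3% to 5.3%.

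**The case against.** The analyses are labelled exploratory and feed no primary or secondary endpoint, sample size or decision. That stands, and it limits the severity.

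A reader might infer that the 7.3 tests will have an inflated error rate. The documents do not support that. Inflation needs both factor and outcome to differ by site, and no site-level rate is given for either. With site rates of 15% to 25% it is negligible. The largest figures combine wide differences in delirium between sites with factors that have 30% to 50% of their variance between sites; nothing in the documents establishes either.

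A reader might also infer that the final models have been shown to select false predictors. They have not. Only univariate tests of a single factor were simulated, with no screen followed by stepwise selection. Other covariates could absorb part of a site difference, and passing a deliberately liberal screen is not a reported finding. For the association with candidate factors, the simulated factor was continuous and normal, so the figures carry over to a categorical variable such as ethnicity only by analogy.

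Finally, the factor list in 7.3 is open-ended and the one-year models are still to be developed, so centre is unspecified rather than excluded. But the named first-step methods have no place for it. Offered only as a candidate, it could also be removed by the p<0.15 screen or by stepwise selection.

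**Conclusion.** The point holds as a conditional one. Section 7.3 prescribes methods without centre for mostly non-randomised exposures across 8 sites, while 7.2 includes centre even in its own non-randomised association, and no reason is given for the difference. Followed as written, 7.3 can report a site difference as an independent predictor, or as an effect of delirium on one-year events.

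The effect ranges from negligible to several times the nominal 5%, depending on site variation that the documents do not report. All figures rest on the assumed ICCs, site spreads and equal site sizes.

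It would be wrong to extend this to the main results: the randomised primary and secondary comparisons include centre and are not affected. This is a cheap improvement, of low to moderate severity because the analyses are exploratory.

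**What to change.** In section 7.3:

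- Keep centre in every univariate and multivariable model, outside the p<0.15 screen and the stepwise selection. Use the centre term of 7.2, as fixed strata or a random effect. If a random effect is chosen, note that it removes between-site confounding only in part unless the factor's site mean is also included.
- Replace 1-way ANOVA and Pearson correlation with linear models that include centre.
- Replace the plain chi-square for delirium against one-year outcomes with a centre-stratified Mantel-Haenszel test, and keep centre in the models that follow.
- Define the term once. Sections 7.1 and 7.2 refer variously to study-centre, study-centre groups and centre-stratum.

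The cost is SAP wording, through the amendment or addendum route in section 9; no new data or change in sample size is needed. Statistically, fixed centre terms use up to 8 − 1 = 7 degrees of freedom, against about 600 × 0.20 = 120 delirium events and a candidate pool that could include the 15 baseline variables of section 5 plus depth, BIS, MAP and MAC. Strata may be sparse for rare one-year events. Factors that vary almost only between sites, as ethnicity might, will have wide intervals; that reflects how little within-site information there is on them.

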3.4 Exploratory Objectives

- To identify demographic, co-morbid and perioperative factors (including anaesthesia depth, BIS, MAP and MAC) that are independently associated with of delirium incidence.
- To identify demographic, co-morbid and perioperative factors (including anaesthesia depth, BIS, MAP and MAC) that are independently associated with severity of delirium.
- To identify demographic, co-morbid and perioperative factors (including anaesthesia depth, BIS, MAP and MAC) independently associated with changes in MMSE score and AMTS levels at 3 and 12 months.
- To test the association between any POD diagnosis and the clinical outcomes, any cardiovascular event (MI, cardiac arrest, stroke, PE) and any infection during 1 year follow-up.

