4 GENERAL ANALYSIS DEFINITIONS

4.1 Treatment Allocation

Participants are randomised in a 1:1 ratio to a BIS of target 50 ('light' anaesthesia) or a BIS of target 35 ('deep' anaesthesia), with randomisation stratified by country.

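### The exploratory predictor models (p<0.15 screen, then stepwise selection, with randomised group competing against achieved BIS and MAC) would often report false independent factors and overstate true ones

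*Combined protocol and SAP*

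**What the plan says.** The aim, in section 3.4, is "To identify demographic, co-morbid and perioperative factors (including anaesthesia depth, BIS, MAP and MAC) that are independently associated with of delirium incidence".

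Section 7.3 gives the method. On the first step it reads: "demographic, co-morbid and perioperative factors (including anaesthesia depth, BIS, MAP and MAC) and POD will be firstly undertaken using univariate logistic regression analyses". Those with p<0.15 go forward, and these "will then be entered into multivariate forward and backward logistic regression models to identify a model containing those measures which are independently associated with POD". Then: "Adjusted Odds ratios and 95% confidence intervals will be derived from these models".

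The same screen and stepwise scheme, with linear models, is planned for delirium severity and for MMSE change and AMTS level.

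The arms are defined in section 4.1 as "a BIS of target 50 ('light' anaesthesia) or a BIS of target 35 ('deep' anaesthesia". The SAP lists anaesthesia depth separately from BIS, so I read depth as the randomised group and BIS as the achieved value. Both readings are inferences, though natural ones.

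Section 7.3 does not give:
- a closed candidate list, or an entry or stay threshold;
- a rule for when the forward and backward models differ;
- a rule for collinear terms;
- a forced term for randomised group or centre;
- any allowance for selection in the estimates or intervals.

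**The concern.** There are two problems.

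First, many candidates are tested against few delirium cases, and the survivors are reported as if the final model had been fixed in advance. Noise factors can then be named as independent predictors. True factors tend to be kept in the samples where they look large, so their odds ratios are overstated.

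Second, achieved BIS and MAC follow from allocation. When they compete with the randomised group, its coefficient no longer estimates the randomised effect, and selection may drop it or put BIS or MAC in its place. A paper could then list achieved BIS as independently associated and leave depth out, and readers would find that hard to set beside the primary analysis.

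**Working it through.** **Size of the dataset.** Section 4.2 gives 25% v 15%, 80% power, two-sided 0.05 and 270 per group. The usual two-proportion formula gives (1.96·√(2·0.20·0.80) + 0.842·√(0.25·0.75 + 0.15·0.85))² / 0.10² = 250 per group. The continuity correction, (250/4)·(1 + √(1 + 4/(250·0.10)))², gives 270, which reproduces the plan's figure. It serves here only to set the number of events:
- 540 patients: 0.25·270 + 0.15·270 = 108 cases.
- 600 patients: 0.25·300 + 0.15·300 = 120 cases.

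**Candidates (assumed).** The 15 baseline variables in section 5 plus depth, BIS, MAP and MAC make 19. Section 7.3 does not refer to that list, so I take a range of 15 to 20. This gives from 108/20 = 5.4 to 120/15 = 8.0 cases per candidate.

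**The screen alone, all candidates null and independent.** The expected number passing p<0.15 is 0.15·15 = 2.25 to 0.15·20 = 3.0. The chance that at least one passes is 1 − 0.85¹⁵ = 91% to 1 − 0.85²⁰ = 96%.

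**Screen plus selection, all null.** If the stay threshold were 0.05, a rough guide is 1 − 0.95¹⁵ = 54% to 1 − 0.95²⁰ = 64%. Simulation of the univariate screen followed by backward elimination (800 to 2,000 runs per setting, about 20% events) agrees:

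| Candidates | Patients | Stay p | At least one false factor |
|---|---|---|---|
| 15 | 600 | 0.05 | 53% |
| 20 | 600 | 0.05 | 63% |
| 19–20 | 540 | 0.05 | 63–65% |
| 15 | 600 | 0.10 | 79% |
| 20 | 600 | 0.10 | 87% |
| 19–20 | 540 | 0.10 | 87–89% |

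**Some true factors.** With 540 patients, five true log odds ratios of 0.25 per SD, 15 null candidates and stay p<0.05, a false factor was kept in 57% of runs. Retained true effects averaged about 0.325, and 0.325/0.25 = 1.30. With weaker effects (0.20, 600 patients, 20 candidates) the overstatement was 30–44% for stay thresholds from 0.15 down to 0.05.

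**Coverage.** In the 0.25 setting, pooled coverage of the reported 95% intervals was about 76%. The reason shows in the 0.20 setting at stay p<0.05, where pooled coverage was 73.1% and 22.7% of reported factors were false. A null term kept because p<0.05 has a Wald interval that must exclude zero, so its coverage is 0%. Coverage for the true factors is therefore 73.1/(100 − 22.7) = 95%. The loss comes from false factors being reported, not from narrow intervals for true ones.

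**Randomised group against BIS and MAC.** A 25% v 15% effect was simulated as acting wholly through allocation, with an assumed arm–BIS correlation of 0.58 or 0.78 in size and MAC also correlated with arm. Fitting BIS and MAC beside arm raised the standard error of the arm coefficient by 32% or 66%. At stay p<0.05, arm was missing from the final model in about 20–30% of runs. Part of this is ordinary lack of power. The log odds ratio is ln(0.25/0.75) − ln(0.15/0.85) = 0.636. Its standard error with 300 per group is √(1/(300·0.25·0.75) + 1/(300·0.15·0.85)) = 0.210, so z = 3.03 and a test of arm alone would miss it 14% of the time. With 270 per group the standard error is 0.221 and the figure is 18%. The effect of the rivals is seen more directly in the runs where BIS or MAC took the place of arm: 8–19% over the correlations tried.

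Forward selection and the linear models for severity, MMSE and AMTS were not simulated.

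**The case against.** The strongest reply is that these analyses are exploratory, in name and in place. The primary comparison in section 7.1 is a stratified Mantel-Haenszel test, and the randomised secondary comparisons in section 7.2 use Mantel-Haenszel tests or linear models with fixed factors. None involves variable selection, so no randomised conclusion rests on section 7.3. This stands, and it limits the severity. It does not remove the point, because the planned output is still a set of factors called independent, with adjusted estimates and 95% intervals.

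The percentages also depend on a candidate count, a stay threshold and a correlation structure that the SAP does not state. This too stands; the figures are ranges under assumptions, and correlated candidates would usually lower the false-factor rate.

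A reader might infer two stronger things:
- *That the intervals for real predictors are too narrow.* They are not, on this evidence: at stay p<0.05 they cover about 95%, although the estimates at their centres are inflated.
- *That a model keeping achieved BIS in place of depth would contradict the trial's result.* It would not. The randomised effect is estimated in section 7.1, and BIS is the quantity that randomisation targets. The risk is of misreading.

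**Conclusion.** The point holds as a minor one, confined to the exploratory models. With 15–20 independent candidates, 108–120 delirium cases and backward elimination, a dataset with no true factors would still give at least one apparently independent factor in about 53–65% of runs at stay p<0.05, and in about 79–89% at stay p<0.10. Retained true log odds ratios of 0.25 would be about 30% too large at stay p<0.05. The candidate number, the thresholds and the independence of the candidates are assumptions; the event rates and patient numbers are the plan's.

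Letting randomised group compete with achieved BIS and MAC is a fault of principle that does not depend on those figures, though it does depend on reading anaesthesia depth as the randomised group. The primary and secondary randomised comparisons are untouched.

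**What to change.** Amend section 7.3, which section 9 allows before database lock:

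- Name the candidate list in advance and remove the p<0.15 univariate screen.
- In the main model for each outcome, keep randomised group and centre stratum whatever their p-values. The last model in section 7.2, relating delirium to later cognition, already includes both.
- Fit the pre-randomisation candidates together with penalisation. Alternatively, bootstrap the whole selection and report selection frequencies and corrected estimates. Either route still serves the aim of identifying factors.
- Put achieved BIS, MAC, MAP and surgical duration in separate models without randomised group, labelled observational. Surgical duration belongs here although section 5 lists it with the baseline variables, because it is known only after surgery.
- Do the same for severity, MMSE and AMTS.

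The cost is new SAP wording, more analysis work and a less parsimonious model. No data collection changes.

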3.3 Secondary Objectives

- To quantify and compare the temporal pattern of the incidence of POD amongst patients undergoing major surgery between those randomised to a BIS of target 50 ('light' anaesthesia) compared with those randomised to a BIS of target 35 ('deep' anaesthesia).
- To quantify and compare the severity of POD amongst patients undergoing major surgery between those randomised to a BIS of target 50 ('light' anaesthesia) compared with those randomised to a BIS of target 35 ('deep' anaesthesia).
- To quantify and compare the change in cognitive function at discharge (or 7 days) post-operatively between randomised groups.
- To quantify and compare the change in cognitive function at 3 and 12 months post-operatively between randomised groups.
- To quantify and compare cognitive impairment at discharge (or 7 days), 3 and 12 months post-operatively between randomised groups.
- To test the associations between POD incidence and subsequent MMSE changes or cognitive impairment and AMTS levels at discharge, or 3 and 12 months.

Secondary endpoints:

1. The incidence of postoperative delirium (POD) on each of the 5 post-operative days.
2. The number of postoperative delirium (POD) episodes over the 5 post-operative days (as a measure of delirium severity).
3. Cognitive change as measured by the Mini-Mental State Examination (MMSE) score at discharge (or 7 days).
4. Cognition level as assessed by modified MMSE (Abbreviated Mental Test Score - AMTS) administered at 3 and 12 months postoperatively by telephone.
5. Cognitive impairment defined as a score on the Mini-Mental State Examination (MMSE) at discharge (or 7 days) as <26 or as an AMTS

score of <8 at 3 and 12 months. Calculated for those with a score ≥ 26 pre-operatively.

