4.2 Sample size calculation

Chan *et al.* showed that delirium incidence was reduced from 24.1% to 15.6% with the use of BIS-guided anaesthesia versus routine care in a broadly similar patient group to the BALANCED Study cohort, with the exception that 83% were ASA 1 or 2. Using the data from Chan *et al.* we hypothesise that the incidence of delirium will be reduced from 25% in the deep anaesthesia group (BIS target 35) to 15% in the light anaesthesia group (BIS target 50). A power analysis using this reduction from 25% to 15%, with power of 80% and two-tailed alpha = 0.05, indicates that approximately 270 patients are required in each group (total of 540 patients). We therefore plan to recruit approximately n=600 patients to allow for all-cause loss-to follow-up.

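### Two non-randomised analyses with delirium as the explanatory variable lack a time-order rule (one-year events) or adjustment for age and case-mix (cognition)

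*Combined protocol and SAP*

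**What the plan says.** **One-year events.** The exploratory objective in section 3.4 reads "To test the association between any POD diagnosis and the clinical outcomes, any cardiovascular event", and goes on to include infection over one year. Section 7.3 gives the method in two steps. First, "any infection during 1 year follow-up will firstly be tested using a chi-square test", and likewise for cardiovascular events. Then multivariable models are built from patient and perioperative factors, and POD is added to them. Section 3.2 defines POD as present if any of ten assessments over five post-operative days is positive.

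**Cognition.** The secondary objective in section 3.3 reads "To test the associations between POD incidence and subsequent MMSE changes or cognitive impairment and AMTS levels". Section 7.2 tests this "using a general linear model which will include randomised group, centre-stratum and" POD diagnosis. It names MMSE change as the only dependent variable, although the same sentence covers AMTS. Cognitive impairment is compared between randomised groups in section 7.2, but no model relates it to POD.

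**What is collected.** Section 5 lists age, ASA status, Charlson score, surgery type, emergency or elective status and pre-operative MMSE among the baseline variables.

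**The concern.** POD is not randomised, so these two analyses lack the protection that the comparison of BIS targets has.

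For the one-year events, the exposure window lies inside the outcome window. The rationale in section 2 itself says that delirium follows many kinds of precipitating factor. A post-operative infection or stroke on day 1 that brings on delirium on day 3 is, as the plan is written, an event in a patient with POD. An association could then reflect events leading to delirium rather than the reverse.

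For cognition, age plausibly drives both POD and later scores. Section 7.3 looks for correlates of POD and of MMSE and AMTS among the same patient factors, which is the structure of confounding. The word subsequent in the objective invites a directional reading. At stake is the interpretation of one secondary and one exploratory objective.

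**Working it through.** **1. The plan's own figure.** The documents give no figure for the disputed analyses. The sample size in section 4.2 supplies N and the POD rate. Inputs: 25% v 15%, 80% power, two-sided 0.05.

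- Uncorrected: n0 = [1.96·√(2·0.20·0.80) + 0.842·√(0.25·0.75 + 0.15·0.85)]² / 0.10² = 250.
- With continuity correction: n = (n0/4)·[1 + √(1 + 4/(n0·0.10))]² = 269.6, so 270 per group.

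This reproduces the plan's figure: "indicates that approximately 270 patients are required in each group (total of 540 patients"). I use N = 540 and, unless stated, a pooled POD rate of 20%.

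**2. Time order, on the text.** POD is fixed by days 1-5 (section 3.2) and the event may occur at any time during one-year follow-up (sections 3.4 and 7.3). No section starts the event count after POD or after day 5, excludes earlier events, or makes POD time-dependent.

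**3. Time order, illustrated (all inputs assumed).** Let e be the proportion with an event before POD, q the POD risk after such an event, 0.18 the POD risk otherwise, and 0.10 the later event risk in everyone else, whatever their POD status. POD therefore has no effect. The cells are:

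- POD, event: a = e·q + (1-e)·0.18·0.10
- POD, no event: b = (1-e)·0.18·0.90
- no POD, event: c = e·(1-q) + (1-e)·0.82·0.10
- no POD, no event: d = (1-e)·0.82·0.90

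OR = ad/(bc); z = ln(OR)/√(Σ 1/(540·cell)).

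| e | q | OR | z |
|---|---|---|---|
| 0.03 | 0.35 | 1.29 | 0.8 |
| 0.03 | 0.50 | 1.56 | 1.5 |
| 0.10 | 0.35 | 1.68 | 2.0 |
| 0.10 | 0.50 | 2.44 | 3.7 |

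Last row: 0.0662·0.6642/(0.1458·0.1238) = 2.44.

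A second assumed grid (one-year event rate 10-30%, 25-75% of events before POD, POD odds raised 1.5 to 3 fold by an early event) gives OR 1.12 to 2.39, with the chi-square rejecting in about 6% to 97% of trials. Its middle case (20%, half, 2 fold) gives OR 1.46 and 32% rejection. Counting only later events, among patients without an earlier one, gives OR 1.00, as it must under these assumptions.

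**4. Confounding by age in MMSE change (assumed inputs).** Let one SD of age raise the log-odds of POD by 0.5 or 0.8, and lower MMSE change by 0.3 or 0.8 points. At 20% POD the mean age gap is 0.48 or 0.73 SD. The spurious POD coefficient is minus the age slope times the gap. With residual SD 2.5, SE = 2.5·√(1/108 + 1/432) = 0.269.

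| log-odds per SD | points per SD | spurious difference | z |
|---|---|---|---|
| 0.5 | 0.3 | -0.14 | -0.5 |
| 0.8 | 0.3 | -0.22 | -0.8 |
| 0.5 | 0.8 | -0.38 | -1.4 |
| 0.8 | 0.8 | -0.58 | -2.2 |

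Only the extreme corner passes 1.96. Adding the age variance to the outcome SD brings it to -2.06.

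**5. Baseline MMSE pulls the other way.** If POD patients start 1 point lower and the baseline-to-follow-up slope is 0.5, regression to the mean shifts change by (1 - 0.5)·1 = +0.5. The net is then -0.14 + 0.5 = +0.36 to -0.58 + 0.5 = -0.08.

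**6. A cognition level, as for AMTS (simulation, 2,000 runs per setting).** With no true POD effect, and age and baseline cognition each shifting POD odds 1.25 to 2 fold and the score 0.1 to 0.4 SD per SD, the section 7.2 model gives a mean POD coefficient of -0.06 to -0.60 SD and false-positive rates of 9% to 100%. The middle case (1.5 fold, 0.2 SD) gives -0.20 SD and 44%. With both covariates added, the mean is about 0.00 and the rate 4.4% to 5.7%. These rates do not carry over to MMSE change.

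**7. Baseline adjustment is not neutral for a change score.** Suppose the groups truly differ by 1 point before surgery and nobody truly changes. The unadjusted difference in change is 0. Adjusted for a baseline of reliability R it is -(1 - R)·1: -0.20 at R = 0.8 and -0.40 at R = 0.6 (R assumed).

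**The case against.** The strongest reply is about scope. Both analyses are observational, the plan speaks of associations throughout, and the one-year event analysis is labelled exploratory. The chi-square is only a first step; the multivariable models that follow can address confounding by patient and perioperative factors. All of that stands. What it leaves open is time order, which covariates recorded before or during surgery cannot repair.

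Several stronger readings are tempting, and the documents do not support them:

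- *That the plan claims effects of delirium.* It does not; an effect is what a reader might take from the result.
- *That events are definitely counted from surgery.* Section 7.3 says only that they occur during one-year follow-up. This is the natural reading, but strictly the start point is unspecified.
- *That every cognition model ignores age.* The section 7.3 factor-finding models of MMSE and AMTS do screen demographic and co-morbid factors. They do not name POD as an exposure, so they do not repair the section 7.2 model.
- *That MMSE change will be biased towards a decline after POD.* Steps 4, 5 and 7 of the working show shifts in both directions.

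A further fair objection is that simply adding pre-operative MMSE to the change-score model exchanges one possible bias for another. This stands and shapes the fix.

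**Conclusion.** The concern holds as a gap in two non-randomised analyses, and it is worth correcting because the correction is cheap. The missing time-order rule, the short covariate list in the section 7.2 POD model and the absent POD-impairment model can all be read directly from the text, and confidence in them is high.

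The size of the bias cannot be established from the documents. They give no event rate, event timing, POD risk after an event, confounder strength or MMSE reliability. The odds ratios and MMSE differences above are illustrations under assumed inputs; at the weaker settings the spurious result would usually not reach significance. For MMSE change the net direction is also unknown.

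A reader might infer that the trial's main result is at risk. It is not: the primary comparison and the randomised secondary comparisons do not use POD as an explanatory variable.

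**What to change.** **Section 7.3, one-year events.** Fix POD status at the end of post-operative day 5. Count only events with onset after that landmark, separately for each outcome, in patients alive and free of that event. Report deaths as a competing outcome. Keep the crude chi-square as description only.

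**Section 7.2, POD and cognition.**
- Write out separate models for MMSE change and for AMTS at 3 and 12 months.
- Add to both age and the co-morbidity and surgery variables from section 5 (for example ASA status, Charlson score, surgery type, emergency status).
- Add pre-operative MMSE to the AMTS models.
- For MMSE change, report results with and without pre-operative MMSE, and say why both are shown.
- Specify a logistic model with the same covariates for POD and cognitive impairment, in patients with pre-operative MMSE of at least 26, as section 3.3 defines that endpoint.

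Report all of these as associations.

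**Cost.** This is SAP wording, and section 9 allows amendment before database lock. The landmark needs event onset dates, assumed to be available, and loses events on days 0-5, so precision falls. The cognition covariates are already listed for collection.
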